- 3) To pilot assess the impact and feasibility of vaccine reminders on HPV vaccination

Methods- This study will utilize a qualitative approach as part of an exploratory sequential design with the primary intent of the exploratory design is to develop a digital tool which will then be tested. We will conduct formative research using key informant interviews with families of preteen/adolescent girls (throughout will be called adolescent) (n=30 dyads/triads), clinicians and immunization nurses of involved study sites (n=10), administrative staff and school leadership of involved study sites (n=12), and leadership within the KCCA and Ministry of Health (n=4) to assess attitudes towards HPV vaccination and text message reminders. Using the results from the interviews we will create prototypes of messages that will be shared with families (n=30 dyads) to identify issues with clarity, tone, and persuasiveness. Next, we will conduct a pilot trial to

randomize caregivers of adolescents at one KCCA site and the adolescent clinic, stratified by site, language and HPV vaccine dose needed (initiation vs. completion). Feasibility milestones will include reach, effect size determination and implementation measures. If the pilot is succesful, we will conduct a future full-scale RCT assessing the impact of the HPV vaccine text message reminders. The main outcome will be timeliness of vaccination. We will also collect process/feasibility measures.

Utility of the Study - The messages will be used for a pilot randomized control trial to examine their impact on HPV vaccination initiation and completion.

Anticipated Study Outcomes- This study will allow us to understand the types of educational information parents and providers believe is needed in HPV vaccination reminders in an LMIC. We will be able to use this information in a future large-scale intervention that will utilize text message reminders to prompt caregivers to return their adolescents for their next HPV dose.

CHAPTER ONE

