We will enroll only one child per family; if more than one is eligible, one will be randomly selected. For the pilot feasibility trial, we will enroll families of girls who are in need of either the first or second dose, with an outcome of receipt of next needed dose. Due to the need to complete the pilot feasibility trial quickly, we will only enroll those in need of the second dose if their next dose is due strictly between 8-20 weeks from enrollment. We will seek written consent from caregivers. We will seek written assent from adolescents of consented caregivers given instead. At enrollment, parents will be verbally administered a demographic and HPV vaccination knowledge and attitude survey.

After enrollment, the Ugandan project coordinator will randomize families into intervention vs. usual care arms (1:1 ratio) stratified by enrollment site, parental language (English or Luganda), and dose due (1st or 2nd) using a randomization module. Research staff will not know the study assignment during enrollment. The outcome assessor and analyst will remain blinded to arm assignments.

Families who report on the demographic survey their highest degree of schooling as P7 or below will be asked at enrollment if, in the case they are randomized to the intervention, they would prefer a voice reminder in lieu of texts; such reminders would include the same content, timing and interactivity as the texts. While in Kampala only 2.1% of women and 0.5% of men have no formal education, 17.6% of women and 17.1% of men completed only some primary school.31 Similarly, families whose daughter is returning to a boarding school and are enrolled at the Adolescent Clinic, health centres, or immunization post will be asked if, in the case they are randomized to the intervention, they want messages sent timed for the next school break. Alternatively, they can select the timing used for those not at boarding school. If the special timing is selected, we will account for the minimal interval between doses (for those in need of a second dose). Intervention-arm families enrolled through Child Days Plus will be sent their series prior to the next Child Days Plus event at their child's school or before any other special immunization day events, if the school holds one.

Intervention, Text Message Target, Content and Frequency:

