For those families randomized to the intervention arm: Based on our previous studies as well as the full country HPV vaccine evaluation highlighting the parents involvement as vaccine decision makers, we plan for the messages to be targeted to the parent, unless in Aim 1 families suggest that girls should also receive the message. All text messages are automated and will be sent in English or Luganda based on parental preference.

The message sequence consists of 5 weekly, main message reminders beginning 5 weeks before the

HPV vaccine dose due date, followed by a series of 2 primary booster messages.(Figure 3). This is based on our previous studies that showed that the median number of messages needed to come in for a vaccine was 5. If enrollment happens more than 4 weeks before the main messages are due to

start, engagement messages will be sent monthly until main messages start. The due date for the vaccine will depend on whether the first (initiation) or second

(completion) dose is due and the enrollment site.

For those who need to initiate vaccination and are:

- *Recruited as part of the school-based program*, the due date will be defined as the next Child Days Plus
- *Recruited in health centre and not in boarding school*, the due date will be defined as 5 weeks after message initiation
- *Recruited in health centre and are in boarding schools,* the due date will be the next school break
- *Recruited in the community*, the due date will be defined as the next HPV vaccination day at the community immunization post that is at least 5 weeks after message initiation

For those who need to complete the vaccination series and are:

- *Recruited as part of the school-based program*, the due date will be defined as the next Child Days Plus
- *Recruited in health centre and not in boarding school*, the due date will be defined as 6 months after the date of the first dose (which is the recommended interval between doses)
- *Recruited in health centre and are in boarding schools,* the due date will be the next school break that is a least 5 months after the date of the first dose, which is the minimal allowed interval between doses
- *Recruited in the community*, the due date will be defined as the next HPV vaccination day at the community immunization post that is at least 5 months after the date of the first dose

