3.5.4 Data management and analysis

Sample Size for Pilot For the feasibility pilot, we will plan to enroll 154 adolescents who are due for an HPV vaccine dose. With a minimal sample size of 77 in each arm, we will be powered to detect a hazards ratio of 1.67 with 80% power, allowing for a 5% type I error comparing time to next dose.

At the study sites, we expect there to be, on average, 1074 girls aged 10-14 in need of vaccination over a 4-month period. We expect 913 families to meet age, language and cell phone/texting inclusion criteria. To meet our minimal sample size of 154 (77/arm) for this pilot/feasibility study, we need to recruit 16.9% of eligible families, which is feasible. If recruitment is slower than expected, we will be able to use more KCCA sites.

Data Management

Vaccination data will be abstracted from the HPV vaccination registers in use clinically at the sites. Girls generally seek care from one site. All data will be entered into a REDCap database hosted at Columbia with secure access provided only to Columbia and Ugandan study staff. The Ugandan-based project coordinator will monitor text messages sent, replies, and "undeliverable" messages under the supervision of Drs. [name] and [name]. Linkages between parents' and girls' information, survey data and vaccine records will be maintained in separate password protected files. All final datasets will be coded.

D10. Analytic Plan

The primary analytic plan for the pilot will focus on feasibility of implementation of the

intervention using a RE-AIM implementation framework (Reach, Effectiveness, Adoption, Implementation, Maintenance). We will focus only on reach, effectiveness, and implementation (not adoption or maintenance which is not applicable for this pilot).

Reach: We will collect data on number of families

- approached
- eligible and ineligible (including reasons for ineligibility)
- eligible who enrolled
- number enrolled in text message vs. phone reminders

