Effectiveness: While the focus of the pilot is on feasibility, we will also assess the effect size of the intervention. The outcome will be timeliness of vaccination (time to event). Time will be from start of main message series to receipt of the next needed dose. Data analysis will be performed using Stata. The primary analysis will be intention-to-treat (ITT), whether or not further messages were declined or undeliverable. A secondary per protocol analysis will only include those who received the entire set of reminders. Timeliness of vaccine receipt will be compared using Kaplan-Meier curves using a stratified log rank test. In addition, in order to gain effect sizes needed for a future large-scale intervention, comparisons will also be stratified assessing those due for the first dose (initiation) and second dose (completion).

Implementation: We will assess various process measures, including:

- Messages sent/delivered (if a text message is electronically returned as undeliverable, we will contact the family using alternative numbers that will be collected at enrollment)
- Number who opted out of further messages
- Number who responded to messages
- Topics families request more information about in reminders
- Factors associated with response and drop out
 - child characteristics (age, site, school status (in or out of school), grade, relationship with caregiver)
 - family characteristics (age, education, employment, income, marital status, distance to health facility, language)

We will also randomly select 30 intervention parents from whom we have received permission in the consent to re-contact. We will conduct a semi-structured interview that will focus on
Page 24 of 142

intervention experiences and suggested changes, and follow the methods and analytic plan outlined under Aim 1. We will also have them complete two implementation measures: Acceptability of Intervention Measure (AIM), Intervention Appropriateness Measure (IAM). These were developed and psychometrically assessed by implementation scientists as consensus measures for *acceptability* and *appropriateness*. In addition, they will also complete an adapted Health Information Technology (IT) Usability Evaluation Scale (Health-ITUES). We will then present findings to key non-parental stakeholders (as identified under Aim 1) and conduct semi-structured interviews to gather feedback. Conduction of the interviews and the analytic plan will follow the methods outlined in Aim 1.

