Statistical Analytic Plan v1.2

Official title: SEARCH: Short Message Service (SMS) Electronic Adolescent Reminders for Completion of HPV Vaccination - Uganda: Pilot

NCT number NCT05151367

Document dates 10/10/2022, 2/6/2023

Aim: To pilot assess the impact and feasibility of vaccine reminders on HPV vaccination

Primary Analysis

The outcome will be timeliness of vaccination (time to event). Time will be from start of main message series to receipt of the next needed dose. For those who did not receive the dose, time will be right censored at 6 months The primary analysis will be intention-to-treat (ITT), whether or not further messages were declined or undeliverable.

Timeliness of vaccine receipt will be compared using Kaplan-Meier curves using a stratified log rank test. In addition, in order to gain effect sizes needed for a future large-scale intervention, comparisons will also be stratified assessing those due for the first dose (initiation) and second dose (completion). It will also be assessed using chi square analyses.

A secondary per protocol analysis will only include those who received the entire set of reminders.

Outcome Variables

- 1) Receipt of by 24 weeks for dose 1 for uninitiated
 - a. Yes, if Day enrollment to HPV dose 1 is < 168 days
 - b. No, if Day enrollment to HPV dose 1 is >= 168 days
 - c. No, if never received
- 2) Receipt of by 24 weeks for dose 2 for initiated
 - a. Yes, if Day enrollment to HPV dose 2 is < 168 days
 - b. No, if Day enrollment to HPV dose 2 is >= 168 days
 - c. No, if never received
- 3) Receipt of by 24 weeks combined
 - d. Yes, if Day enrollment to next needed dose (1st or 2nd depending on if initiated or uninitiated) is < 168 days

- a. No, if Day enrollment to next needed dose (1st or 2nd depending on if initiated or uninitiated) is >= 168 days
- b. No, if never received

Analyses:

- 1. Chi square of randomization group by 24 week variables
- 2. Calculate relative "risk"
- 3. Check for interaction term by language and by site for randomization (separately)
- 4. Calculate number needed to treat for one additional vaccination by 24 weeks for dose 1, dose 2 or either (combined variable)
- 5. Run Kaplan-Meier curve. Outcomes are the 24 week variables.

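### The pilot is sized on a hazard ratio and meant to yield effect sizes, but no hazard ratio is a named output, no confidence interval is planned, and the 24-week analyses ignore the randomisation strata

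*SAP*

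**What the plan says.** **Purpose.** The protocol Abstract (Methods) states: "Feasibility milestones will include reach, effect size determination and implementation measures". Section 3.5.4 (Effectiveness) and the SAP (Primary Analysis) both add comparisons by dose due, "in order to gain effect sizes needed for a future large-scale intervention".

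**Sizing.** Section 3.5.4 says that with 77 per arm the trial is "powered to detect a hazards ratio of 1.67 with 80% power" at 5% type I error.

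**Time-to-event output.** Protocol and SAP plan the same comparison: "Timeliness of vaccine receipt will be compared using Kaplan-Meier curves using a stratified log rank test". Neither names the strata, a hazard model, or an HR to be reported.

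**24-week output.** The SAP (Analyses) lists a chi-square by arm, a relative risk, interaction checks by language and by site, an NNT for dose 1, dose 2 and combined, and a Kaplan-Meier curve on the 24-week variables. No interval is stated for any of them. The only CI in either document belongs to a cited review (protocol 2.0).

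**Randomisation.** Section 3.5.3 randomises 1:1, stratified by enrolment site, parental language and dose due.

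**The concern.** The main product of this pilot for the next trial is an effect estimate with its uncertainty. As written, the time-to-event comparison gives curves and a p-value, and the 24-week comparison gives point estimates only. The quantity used for sizing is not among the planned outputs. The model, strata, tie handling and intervals would be chosen after the data are seen. A bare point estimate from 154 families, or about half that number within a dose group, could be carried into a sample size calculation as if it were precise.

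A lesser matter is that the primary test is stratified and the 24-week analyses are not. The combined variable ignores site, language and dose. The dose-specific variables ignore site and language.

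**Working it through.** **1. The plan's own figure.** Inputs from 3.5.4: HR 1.67, 80% power, 5% type I error (two-sided assumed), 154 girls.
- Events needed (Schoenfeld) = 4(1.960 + 0.842)² / (ln 1.67)² = 119.4, so 120.
- 120/154 = 77.9% of girls would need the event.
- The sizing paragraph gives no event proportion, so 154 cannot be reproduced from its own inputs. If control uptake is taken as 69.8% (the clinic's completion figure without a time limit, protocol 2.0), the treated proportion is 1 − 0.302^1.67 = 0.865, the mean is 0.781, and 120/0.781 = 153.6, so 154. That match rests on the assumption.

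**2. The HR interval the plan does not ask for.** Take control uptake as 30.2%, the clinic's six-month completion figure in 2.0. It is a second-dose figure, so using it here is an assumption.
- Treated uptake = 1 − (1 − 0.302)^1.67 = 0.451.
- Events = 77(0.302 + 0.451) = 58.0.
- SE(log HR) = 2/√58.0 = 0.263.
- 95% CI = 1.67 ×/÷ exp(1.96 × 0.263) = **1.00 to 2.79**.
- One dose group, if doses split evenly with equal uptake: 29.0 events, SE = 2/√29.0 = 0.371, CI 0.81 to 3.46.

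The same formula at other assumed control uptakes:

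| Control uptake | Events | 95% CI, all girls |
|---|---|---|
| 20% | 39.4 | 0.89 to 3.12 |
| 40% | 75.0 | 1.06 to 2.63 |
| 60% | 106.5 | 1.14 to 2.44 |
| 69.8% | 120.3 | 1.17 to 2.39 |

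**3. Intervals for RR and NNT**, at 30.2% against 45.1%, 77 per arm.
- RR = 1.49; SE(log RR) = √[0.698/(77 × 0.302) + 0.549/(77 × 0.451)] = 0.214; CI 0.98 to 2.27.
- Risk difference = 14.9 points; SE 7.7 points; CI −0.2 to 30.1.
- NNT = 1/0.149 = 6.7. Its interval runs from 3.3 through infinity, so it should be read from the risk difference.

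**4. Ignoring the strata.** The crude chi-square uses variance p̄(1 − p̄). The stratified test uses the average of p(1 − p) within strata. The ratio shows how conservative the crude test is.
- Two sites at 30.2% and 10.5%: 0.2035 × 0.7965 = 0.1621 against (0.2108 + 0.0940)/2 = 0.1524; ratio 1.06.
- Two sites at 30.2% and 40.5%: 0.3535 × 0.6465 = 0.2285 against (0.2108 + 0.2410)/2 = 0.2259; ratio 1.01.
- Equal rates: ratio 1.

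Simulated power change from crude chi-square to Cochran-Mantel-Haenszel (100,000 trials per scenario, true HR 1.67, 77 per arm):

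| Scenario | Change in power (points) |
|---|---|
| Clinic 30.2% plus one health centre at 40.5% | +0.6 to +0.8 |
| Clinic 30.2% plus one health centre at 10.5% | +2.5 to +2.8 |
| Four sites at 10.5, 25 (assumed), 40.5 and 30.2%; 16 strata | +2.4 to +2.9 |
| No differences; 2, 8 or 16 strata | −0.3 to −1.1 |

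The site rates are second-dose completion figures from 2.0, used only as a spread; their time windows do not match the trial's.

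**5. Whether a stratified Cox model is workable.** One health centre plus the clinic (Abstract) gives 2 × 2 × 2 = 8 strata. Three health centres plus the clinic (3.2, 3.5.3) give 4 × 2 × 2 = 16, or 154/16 = 9.6 girls per stratum. In 1,500 simulated trials per layout at 30.2% uptake with no stratum differences, the stratified model's SE was 0.4 to 2.0% above the unstratified one, and interval coverage was 94.9 to 95.7%.

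**The case against.** **The planners can recover what is missing.** They are the same team, and both institutions keep the analytic dataset (protocol, Data Sharing). An approximate HR follows from the log-rank counts, and intervals for RR and risk difference follow from the 2×2 tables. This stands. A reader might infer that the larger trial could not be sized from this pilot, or that no effect size is planned. The documents do not support either: RR and NNT are planned, by dose and combined. The gap is that the HR and all intervals are left to later choice.

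**It is a feasibility pilot, and nothing is biased.** True. The primary log-rank test is stratified, and the crude RR is unbiased under 1:1 stratified allocation. The crude chi-square is conservative, not anti-conservative, and only if uptake differs between strata. Feasibility focus does not remove the need for precision, because effect size is itself a listed milestone.

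**A larger gain from stratifying might be inferred.** Pairing sites at 10.5% and 40.5% gives about +6 to +7 points. Those are the extremes among three health centres, and no section describes a trial run at that pair alone, so the figure is not used.

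**The time windows might seem to add to the size of this point.** The SAP starts the time-to-event clock at the message series ("Time will be from start of main message series to receipt of the next needed dose") but counts the 24-week variables from enrolment ("Yes, if Day enrollment to HPV dose 2 is < 168 days"). Second-dose girls enter 8 to 20 weeks before their due date, so the windows differ. That is a separate matter to reconcile. SAP analysis 5 runs Kaplan-Meier on the 24-week variables, so the two may have been meant to share a window. Any figure for the gap also needs an assumed hazard shape, and a constant hazard is doubtful when due dates cluster.

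**Conclusion.** The point holds as a matter of incomplete specification that should be corrected; it does not invalidate the trial. The plan sizes on an HR and promises effect sizes, but names no HR and no interval.

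The size of what goes unreported is an HR interval of about 1.00 to 2.79 at an assumed 30.2% control uptake, and 0.89 to 3.12 or 1.14 to 2.44 at 20% or 60%. These widths assume proportional hazards, equal arms and an observed HR of 1.67. The fix reports them and does not narrow them.

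The strata point is lesser: about +0.6 to +2.9 power points for moderate site differences, and a loss of about 1 point or less if there are none.

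**What to change.** Amend the SAP (Primary Analysis and Analyses):

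- **(a)** Name the log-rank strata. Add a Cox model stratified by the same factors (site, language and dose overall; site and language within dose). Report HR with 95% CI overall and by dose. Use Efron's method for ties, because due dates cluster on Child Days Plus and school breaks (protocol 3.5.3).
- **(b)** Report 95% CIs for the 24-week RR and risk difference, and take the NNT from the risk difference.
- **(c)** As a lesser improvement, use Cochran-Mantel-Haenszel tests and Mantel-Haenszel RR and risk difference stratified by the randomisation factors. Fix in advance a rule for pooling sparse strata, and keep the crude results as descriptive.

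A proportional-hazards check and early- and late-period HRs are optional.

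**Cost.** SAP wording and a few lines of Stata. All strata are recorded at randomisation, so no new data or participants are needed. If strata do not differ, the Cox SE is 0.4 to 2.0% larger and Cochran-Mantel-Haenszel loses about 1 power point or less. Parts (a) and (b) alone would close the main gap.

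### The SAP times vaccination from main-message start in the primary analysis but from enrollment in the 24-week variables, and it assigns Kaplan-Meier to both

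*SAP*

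**What the plan says.** **Time-to-event clock.** The SAP (Primary Analysis) and Protocol 3.5.4 (Effectiveness) use the same sentence: "Time will be from start of main message series to receipt of the next needed dose". The SAP adds: "For those who did not receive the dose, time will be right censored at 6 months". Kaplan-Meier curves and a stratified log-rank test are specified on this outcome. The SAP then says of it: "It will also be assessed using chi square analyses".

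**24-week clock.** Under Outcome Variables, the SAP defines three yes/no variables (dose 1, dose 2, combined), all counted from enrollment. For the second dose: "Yes, if Day enrollment to HPV dose 2 is < 168 days". Under Analyses, items 1 and 4 use these variables for chi-square and NNT. Item 2, relative risk, sits between them and names no other variable. Item 5 reads: "Run Kaplan-Meier curve. Outcomes are the 24 week variables".

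**Gap between the clocks.** Protocol 3.5.3 restricts second-dose entry: "we will only enroll those in need of the second dose if their next dose is due strictly between 8-20 weeks from enrollment". It also says: "The message sequence consists of 5 weekly, main message reminders beginning 5 weeks before the" due date. For first-dose girls recruited at a health centre and not in boarding school, "the due date will be defined as 5 weeks after message initiation".

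**Follow-up.** Protocol 3.5.3 gives each girl a 6-month observation period without saying when it starts. The Study timeline puts enrollment in months 7-10 and outcome observation in months 8-16.

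**The concern.** A binary endpoint may have its own start point if it is labelled as a separate endpoint. Here it is not. The SAP presents chi-square as another assessment of the same timeliness outcome and then names the enrollment-based variables as the Kaplan-Meier outcomes, without a time axis. Kaplan-Meier therefore has two specifications, and the analyst must choose between them, possibly after seeing the data.

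Both documents say the dose-specific comparisons are meant to supply effect sizes for a larger trial. A second-dose relative risk or NNT on the 168-day rule averages over girls with very different amounts of time after their reminders began, and it can classify a girl differently from the log-rank test.

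Two gaps make this harder to settle from the text:
- Usual-care families receive no messages, and no start date is assigned to them. For first-dose health-centre girls it cannot be worked back, because their due date is itself defined from message initiation.
- Because the observation period has no stated origin, censoring every unvaccinated girl at 6 months from message start may credit time that nobody observed.

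**Working it through.** The documents give no figure that depends on the choice of clock. The sample-size statement (Protocol 3.5.4) gives HR 1.67, 80% power and 77 per arm but no uptake rate, so it does not reveal which window was intended.

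**1. Window arithmetic, second dose.** Let *d* be weeks from enrollment to due date, 8 to 20 (limiting values, since the bounds are exclusive).
- Message start = *d* − 5 = week 3 to 15.
- Message start to day 168 = 24 − (*d* − 5) = 21 down to 9 weeks.
- Due date to day 168 = 24 − *d* = 16 down to 4 weeks.

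**2. A discordant case.** A girl due at week 14 has message start at week 9. Vaccinated at week 25 (day 175), she is 16 weeks past message start, so she is a log-rank event. Since 175 ≥ 168, she is a chi-square *No*. This holds even if follow-up ends 26 weeks after enrollment.

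**3. First dose.** Health-centre girls whose messages start at enrollment lose only 26 − 24 = 2 weeks. The 8-20 week limit does not apply to first-dose girls. If the next Child Days Plus were 26 weeks away (assumed from two a year), messages would start at week 21, leaving 3 weeks before day 168, and the due date would fall 2 weeks after it.

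**4. Timeline.** A second-dose girl enrolled at the end of month 10 has message start at month 10.7 to 13.4 and reaches 6 months at month 16.7 to 19.4, beyond month 16. If registers were read only to the end of month 16 and enrollment were uniform, about 51-68% of second-dose girls would fall short of 6 months from message start. Those who fall short would do so by about 5 weeks on average and up to 15.

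**5. Size for second-dose girls.** Assumptions: HR 1.67, due dates uniform over 8-20 weeks, no dose before message start. With cumulative hazard *H*(*w*) at *w* weeks after message start, control risk = 1 − exp(−*H*) and intervention risk = 1 − exp(−1.67*H*), averaged over *d*. NNT = 1/(risk difference), from unrounded risks.

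- *Time-framed uptake* (Protocol 2.0: 30.2% within 6 months, 36.5% within 12): *H*(5) = −ln 0.698 = 0.360, then −ln(0.635/0.698)/26 = 0.0036 per week.
- *Constant hazard* with an assumed 26-week control risk *p*: rate = −ln(1 − *p*)/26. For *p* = 30.2% this is 0.0138 per week.

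Risks are control/intervention:

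| Uptake | Day 168 from enrollment | 26 wk from enrollment | 26 wk from message start |
|---|---|---|---|
| Time-framed | 0.327/0.484, RR 1.480, NNT 6.4 | 0.332/0.490, RR 1.477, NNT 6.3 | 0.353/0.517, RR 1.464, NNT 6.1 |
| Constant, 12% | 0.071/0.116, RR 1.628, NNT 22.4 | 0.080/0.130, RR 1.623, NNT 20.0 | 0.120/0.192, RR 1.602, NNT 13.8 |
| Constant, 30.2% | 0.186/0.291, RR 1.559, NNT 9.6 | 0.209/0.323, RR 1.546, NNT 8.8 | 0.302/0.451, RR 1.495, NNT 6.7 |
| Constant, 70% | 0.494/0.675, RR 1.366, NNT 5.5 | 0.539/0.722, RR 1.339, NNT 5.5 | 0.700/0.866, RR 1.237, NNT 6.0 |

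The share of control events that the 168-day rule scores *No* is 1 − (column 1 risk)/(longer-window risk). In row order it is 1.5%, 11%, 11% and 8% against 26 weeks from enrollment, and 7.5%, 41%, 38% and 29% against 26 weeks from message start. With a month-16 cut-off it lies between about 5% and 35%.

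The Protocol does not tie its 12% or 69.8% completion figures to a 26-week window, so the constant-hazard rows show a range and not a forecast.

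**The case against.** **The 24-week variables are a legitimate endpoint.** They are explicitly defined from a date every girl in both arms has, and chi-square and NNT on them can be computed as written. This stands as far as it goes: labelling them as a separate endpoint would remove that part of the conflict. The SAP does not do so, and it offers chi-square as a further assessment of timeliness.

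**Item 5 may only list which events to plot**, with the time axis taken from Primary Analysis. That reading is possible, but it leaves open whether a dose after day 168 counts as an event.

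**The large differences come from the less supported scenarios.** This is fair. The Study timeline fits 6 months from enrollment better, and on that window with the time-framed rates only 1.5% of control events change class. Constant hazard also ignores clustering at fixed dates such as Child Days Plus, which for second-dose girls fall inside the 168 days. Sampling error is far larger than a shift from 6.4 to 6.3: with 32.7% against 48.4% and all 77 per arm, the 95% interval for the risk difference is about 0.004 to 0.31, and second-dose girls are only a subset.

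**The figures assume no dose before message start.** They do. For health-centre girls not in boarding school this is largely supported: messages begin about 26 − 5 = 21 weeks after dose 1, and the Protocol's minimum interval is 5 months.

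These points limit the numerical stakes. They do not tell the analyst which Kaplan-Meier analysis to run or which start date a usual-care girl has.

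**Conclusion.** The concern holds and should be fixed. As written, the plan does not determine the time-to-event analysis: there are two origins, two horizons (6 months and 168 days), two descriptions of Kaplan-Meier, and no origin for the control arm. The 9-to-21-week spread in second-dose post-message follow-up follows directly from the Protocol's own rules.

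The effect on the estimates is uncertain because the documents give neither a usual-care uptake curve nor a follow-up origin. It ranges from negligible with the time-framed rates to substantial under a low constant hazard with full follow-up from message start. Across the scenarios, the 168-day rule raises the relative risk by 0.003-0.03 against 26 weeks from enrollment and by 0.02-0.13 against 26 weeks from message start. NNT can move either way. Both arms share each clock, so no fixed direction of bias is claimed. The feasibility measures, which are the pilot's focus, are unaffected.

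**What to change.** State one origin and one length for the log-rank, Kaplan-Meier, chi-square, relative risk and NNT, and bring the SAP, Protocol 3.5.3 and 3.5.4, and the Study timeline into line. There are two workable choices:

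- **(a) Scheduled main-message start**, assigned at randomization in both arms, with a stated rule that keeps doses given before that date in the intention-to-treat set. This needs one stored date per usual-care girl. Late enrollees are censored earlier unless abstraction continues up to about 3.5 months past month 16 (15 weeks).
- **(b) Enrollment or randomization throughout**, amending the stated time origin in the SAP and one sentence in Protocol 3.5.4. This needs no new data but accepts unequal post-message windows for second-dose girls (9-21 weeks with a 24-week horizon).

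Under either choice:
- Run Kaplan-Meier and the log-rank test on the time variable, not on the yes/no variables.
- Censor girls without a dose at the earlier of the horizon and their last register abstraction. Sites are already visited every 2-4 weeks.
- Where anyone is censored before the horizon, take relative risk and NNT from the Kaplan-Meier risks.
- Report the other clock as a labelled sensitivity analysis.
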